Appendix 2. Description of Efficacy Analyses

The table below provides the detailed analyses including estimand strategy, analysis method, missing data imputation, analysis population, and analysis type.

Measure	Endpoint	Estimand Strategy	Analysis Population	Comparison/ Timepoint	Analysis Method	Analysis Type
SLEDAI	SLEDAI-4	Composite	mITT	LY3471851 vs Placebo at postbaseline visits in the treatment period	Logistic Regression with NRI; Fisher’s Exact Test with NRI	Logistic Regression with NRI for Week 24 – Primary Other – Exploratory
		Composite	Per-Protocol	LY3471851 vs Placebo at postbaseline visits in the treatment period	Logistic Regression with NRI; Fisher’s Exact Test with NRI	Exploratory
		Treatment Policy	mITT	LY3471851 vs Placebo at postbaseline visits in the treatment period	Logistic Regression with NRI; Fisher’s Exact Test with NRI	Exploratory
	No worsening from baseline in SLEDAI-2K	Composite	mITT	LY3471851 vs Placebo at postbaseline visits in the treatment period	Logistic Regression with NRI; Fisher’s Exact Test with NRI	Exploratory
	SLEDAI Change from Baseline	Hypothetical	mITT	LY3471851 vs Placebo at postbaseline visits in the treatment period	MMRM	Exploratory
		Composite	mITT	LY3471851 vs Placebo at postbaseline visits in the treatment period	MMRM with BOCF	Exploratory
	Individual Organ Domain Improvement Defined by SLEDAI-2K	Composite	mITT – Patients with SLEDAI-2K score > 0 within the organ domain at baseline	LY3471851 vs Placebo at postbaseline visits in the treatment period	Logistic Regression with NRI; Fisher’s Exact Test with NRI	Exploratory
	Individual Organ Domain Worsening Defined by SLEDAI-2K	Composite	mITT – Patients with at least one baseline SLEDAI-2K = 0 in the organ domain at baseline	LY3471851 vs Placebo at postbaseline visits in the treatment period	Logistic Regression with NRI; Fisher’s Exact Test with NRI	Exploratory

Measure	Endpoint	Estimand Strategy	Analysis Population	Comparison/ Timepoint	Analysis Method	Analysis Type
	Resolution of Arthritis and/or Rash by SLEDAI-2K Components	Composite	mITT – Patients with SLEDAI-2K arthritis and/or rash ‘Present’ at baseline	LY3471851 vs Placebo at postbaseline visits in the treatment period	Logistic Regression with NRI; Fisher’s Exact Test with NRI	Logistic Regression with NRI for Week 24 – Secondary Other – Exploratory
SRI-4	SRI-4	Composite	mITT	LY3471851 vs Placebo at postbaseline visits in the treatment period	Logistic Regression with NRI; Fisher’s Exact Test with NRI	Logistic Regression with NRI for Week 24 – Secondary Other – Exploratory
		Composite	Per-Protocol	LY3471851 vs Placebo at postbaseline visits in the treatment period	Logistic Regression with NRI; Fisher’s Exact Test with NRI	Exploratory
BICLA	BICLA	Composite	mITT – Patients with at least 1 BILAG A or 2 BILAG B scores at baseline	LY3471851 vs Placebo at postbaseline visits in the treatment period	Logistic Regression with NRI; Fisher’s Exact Test with NRI	Logistic Regression with NRI for Week 24 – Secondary Other – Exploratory
		Composite	Per-Protocol – Patients with at least 1 BILAG A or 2 BILAG B scores at baseline	LY3471851 vs Placebo at postbaseline visits in the treatment period	Logistic Regression with NRI; Fisher’s Exact Test with NRI	Exploratory
LLDAS	LLDAS	Composite	mITT	LY3471851 vs Placebo at postbaseline visits in the treatment period	Logistic Regression with NRI; Fisher’s Exact Test with NRI	Logistic Regression with NRI for Week 24 – Secondary Other – Exploratory

Measure	Endpoint	Estimand Strategy	Analysis Population	Comparison/ Timepoint	Analysis Method	Analysis Type
BILAG	BILAG Improvement	Composite	mITT – Patients with at least 1 BILAG A or 2 BILAG B at baseline	LY3471851 vs Placebo at postbaseline visits in the treatment period	Logistic Regression with NRI Fisher’s Exact Test with NRI	Exploratory
	BILAG No Worsening	Composite	mITT	LY3471851 vs Placebo at postbaseline visits in the treatment period	Logistic Regression with NRI Fisher’s Exact Test with NRI	Exploratory
	Individual Organ Domain - Improvement Defined by BILAG	Composite	mITT – Patients with BILAG A or B within the organ domain at baseline	LY3471851 vs Placebo at postbaseline visits in the treatment period	Logistic Regression with NRI Fisher’s Exact Test with NRI	Exploratory
	Individual Organ Domain - No Worsening Defined by BILAG	Composite	mITT – Patients with no BILAG A within the organ domain at baseline	LY3471851 vs Placebo at postbaseline visits in the treatment period	Logistic Regression with NRI Fisher’s Exact Test with NRI	Exploratory
PGA	PGA Change from Baseline	Hypothetical	mITT	LY3471851 vs Placebo at postbaseline visits in the treatment period	MMRM	Exploratory

Measure	Endpoint	Estimand Strategy	Analysis Population	Comparison/ Timepoint	Analysis Method	Analysis Type
		Composite	mITT	LY3471851 vs Placebo at postbaseline visits in the treatment period	MMRM with BOCF	Exploratory
	No worsening in PGA	Composite	mITT	LY3471851 vs Placebo at postbaseline visits in the treatment period	Logistic Regression with NRI Fisher's Exact Test with NRI	Exploratory
	PGA ≤1	Composite	mITT – Patients with PGA > 1 at baseline	LY3471851 vs Placebo at postbaseline visits in the treatment period	Logistic Regression with NRI Fisher's Exact Test with NRI	Exploratory

[figure not shown]
A large, stylized red logo consisting of the letters 'C', 'C', and 'I' in a serif font, positioned in the upper left quadrant of a large black rectangular area that covers most of the page.

CCI

Abbreviations: Anti-dsDNA = anti-double stranded deoxyribonucleic acid; BICLA = British Isles Lupus Assessment Group-based Composite Lupus Assessment; BILAG = British Isles Lupus Assessment Group - 2004; BOCF = baseline observation carried forward; CCI [REDACTED] FACIT-Fatigue = Functional Assessment of Chronic Illness Therapy – Fatigue Scale; LLDAS = Lupus Low Disease Activity State; mITT = modified intent-to-treat; MMRM = mixed models for repeated measures; NRI = nonresponder imputation; PGA = Physician Global Assessment; CCI [REDACTED] SF = Short Form; SF-36 = 36-Item Short Form Health Survey; CCI [REDACTED] SLE = systemic lupus erythematosus; SLEDAI-2K = Systemic Lupus Erythematosus Disease Activity Index 2000; SLEDAI-4 = a ≥ 4 -point reduction in SLEDAI-2K score from baseline; SLICC = Systemic Lupus Erythematosus International Collaborating Clinics; SRI-4 = Systemic Lupus Erythematosus Responder Index-4.

Appendix 3. Corticosteroid

All corticosteroid doses need to be converted to prednisone equivalent doses (as detailed in Section 6.9). If additional conversion factors are required, these will be added to the table below in a statistical analysis plan amendment prior to database lock.

The following table should be used for converting nonprednisone medications to prednisone equivalent:

Multiply the dose of the corticosteroid taken by the patient (in milligrams) in Column 1 by the conversion factor in Column 2 to get the equivalent dose of prednisone (in milligrams).

*Example: Patient is taking 16 mg of methylprednisolone po daily.
To convert to prednisone: $16 \text{ mg methylprednisolone} \times 1.25 = 20 \text{ mg prednisone}$. 16 mg of methylprednisolone po daily is equivalent to 20 mg of prednisone po daily.*

Column 1	Column 2
	

Appendix 4. List of MedDRA Preferred Terms for Potential Opportunistic Infections (POI)

Category	Potential Opportunistic Infection	Preferred Term (MedDRA Version 22.1)	Preferred Term Code	Lilly Defined Classification
Mycobacterial/ Actino	Nocardiosis (II)	Nocardia sepsis	10064952	Narrow
		Nocardiosis	10029444	
		Nocardia test positive	10070131	Broad
Mycobacterial/ Actino	Nontuberculous mycobacterium disease (II)	Atypical mycobacterial infection	10061663	Narrow
		Atypical mycobacterial lower respiratory tract infection	10075026	
		Atypical mycobacterial lymphadenitis	10003755	
		Atypical mycobacterium pericarditis	10055036	
		Atypical mycobacterial pneumonia	10071075	
		Borderline leprosy	10006029	
		Bovine tuberculosis	10006049	
		Indeterminate leprosy	10021700	
		Leprosy	10024229	
		Lepromatous leprosy	10024227	
		Mycobacterial infection	10062207	
		Mycobacterial peritonitis	10073514	
		Mycobacterium abscessus infection	10064789	
		Mycobacterium avium complex immune restoration disease	10058449	
		Mycobacterium avium complex infection	10058806	
		Mycobacterium chelonae infection	10071401	
		Mycobacterium fortuitum infection	10049659	
		Mycobacterium kansasii infection	10028447	
		Mycobacterium marinum infection	10028452	
		Mycobacterium ulcerans infection	10066289	

Category	Potential Opportunistic Infection	Preferred Term (MedDRA Version 22.1)	Preferred Term Code	Lilly Defined Classification
		Superinfection mycobacterial	10075381	
		Tuberculoid leprosy	10044729	
		Type 1 lepra reaction	10070516	
		Type 2 lepra reaction	10070517	
		Atypical mycobacterium test positive	10070326	Broad
		Mycobacterial disease carrier	10075025	
		Mycobacterium leprae test positive	10070324	
		Mycobacterium test	10070407	
		Mycobacterium test positive	10070323	
		Ureaplasma ulvovaginitis	10081280	
Mycobacterial/ Actino	Tuberculosis (I)	Adrenal gland tuberculosis	10001358	Narrow
		Bone tuberculosis	10056377	
		Choroid tubercles	10008779	
		Congenital tuberculosis	10010657	
		Conjunctivitis tuberculous	10010754	
		Cutaneous tuberculosis	10011684	
		Disseminated Bacillus Calmette-Guerin infection	10076666	
		Disseminated tuberculosis	10013453	
		Ear tuberculosis	10014027	
		Epididymitis tuberculous	10015004	
		Extrapulmonary tuberculosis	10064445	
		Female genital tract tuberculosis	10061150	
		Immune reconstitution inflammatory syndrome associated tuberculosis	10072797	
		Intestinal tuberculosis	10075268	
		Joint tuberculosis	10056367	
		Lupus vulgaris	10025143	
		Lymph node tuberculosis	10025183	

Category	Potential Opportunistic Infection	Preferred Term (MedDRA Version 22.1)	Preferred Term Code	Lilly Defined Classification
		Male genital tract tuberculosis	10061234	
		Meningitis tuberculous	10027259	
		Oesophageal tuberculosis	10030200	
		Oral tuberculosis	10076879	
		Pericarditis tuberculous	10055069	
		Peritoneal tuberculosis	10053583	
		Prostatitis tuberculous	10064743	
		Pulmonary tuberculoma	10066927	
		Pulmonary tuberculosis	10037440	
		Renal tuberculosis	10038534	
		Salpingitis tuberculous	10039463	
		Silicotuberculosis	10068876	
		Spleen tuberculosis	10041640	
		Thyroid tuberculosis	10043774	
		Tuberculoma of central nervous system	10052883	
		Tuberculosis	10044755	
		Tuberculosis bladder	10044758	
		Tuberculosis gastrointestinal	10061390	
		Tuberculosis liver	10058120	
		Tuberculosis of central nervous system	10061391	
		Tuberculosis of eye	10044819	
		Tuberculosis of genitourinary system	10044828	
		Tuberculosis of intrathoracic lymph nodes	10044846	
		Tuberculosis of peripheral lymph nodes	10044965	
		Tuberculosis ureter	10045026	
		Tuberculous abscess central nervous system	10052884	
		Tuberculous endometritis	10071559	
		Tuberculous laryngitis	10045072	
		Tuberculous pleurisy	10045104	
		Tuberculous tenosynovitis	10059161	
		Interferon gamma release assay	10073542	Broad

Category	Potential Opportunistic Infection	Preferred Term (MedDRA Version 22.1)	Preferred Term Code	Lilly Defined Classification
		Interferon gamma release assay positive	10072866	
		Mycobacterium tuberculosis complex test	10070472	
		Mycobacterium tuberculosis complex test positive	10070325	
		Tuberculid	10044725	
		Tuberculin test	10044726	
		Tuberculin test false negative	10074840	
		Tuberculin test positive	10044728	
Bacteria	Bartonellosis (disseminated disease only) (V)	Bacillary angiomatosis	10003971	Narrow
		Trench fever	10044582	
		Bartonella test	10075209	Broad
		Bartonella test positive	10070157	
		Bartonellosis	10004145	
		Cat scratch disease	10007729	
		Peliosis hepatis	10034229	
		Splenic peliosis	10068851	
	Campylobacteriosis (invasive disease only) (V)	Campylobacter sepsis	10070681	Narrow
		Campylobacter colitis	10076769	Broad
		Campylobacter gastroenteritis	10007048	
		Campylobacter infection	10051226	
		Campylobacter test positive	10070025	
	Legionellosis (II)	Legionella infection	10061266	Narrow
		Pneumonia legionella	10035718	
		Pontiac fever	10054161	
Legionella test		10070410	Broad	
Legionella test positive		10070092		
Bacteria	Listeria monocytogenes (invasive disease only) (II)	Listeria encephalitis	10054116	Narrow
		Listeria sepsis	10063085	
		Meningitis listeria	10027248	
		Listeria test	10075707	Broad
		Listeria test positive	10070094	
		Listeriosis	10024641	
	Salmonellosis (invasive disease only) (II)	Aortitis salmonella	10074937	Narrow
		Arthritis salmonella	10003271	
		Meningitis salmonella	10027254	
		Osteomyelitis salmonella	10031262	
		Paratyphoid fever	10033971	

Category	Potential Opportunistic Infection	Preferred Term (MedDRA Version 22.1)	Preferred Term Code	Lilly Defined Classification
		Pneumonia salmonella	10035733	Broad
		Salmonella bacteraemia	10058924	
		Salmonella sepsis	10058878	
		Typhoid fever	10045275	
		Salmonella test positive	10070127	
		Salmonellosis	10039447	
		Salmonella test	10079854	
Bacteria	Shigellosis (invasive disease only) (V)	Shigella sepsis	10074481	Narrow
		Shigella infection	10054178	Broad
		Shigella test positive	10070129	
	Vibriosis (invasive disease due to V. vulnificus) (V)	Gastroenteritis vibrio	10017917	Broad
		Vibrio test positive	10070161	
		None		Narrow
	Infective Pneumonia SMQ	Pneumonia acinetobacter	10079866	Narrow
		Pneumonia proteus	10079867	
		Pneumonia serratia	10079868	
Fungal	Aspergillosis (invasive disease only) (II)	Aspergillosis oral	10003489	
		Cerebral aspergillosis	10051597	
		Meningitis aspergillus	10073245	
		Oro-pharyngeal aspergillosis	10053029	
		Aspergillus infection	10074171	
		Aspergillus test	10070450	
		Aspergillus test positive	10070448	
		Bronchopulmonary aspergillosis	10006473	
		Sinusitis aspergillus	10051016	
	Blastomycosis (IV)	Blastomycosis	10005098	Narrow
		Epididymitis blastomyces	10015001	
		Osteomyelitis blastomyces	10031255	
		Pneumonia blastomyces	10035671	
		None		Broad
	Candidiasis (invasive disease, or oral not limited to the tongue) (II)	Candida endophthalmitis	10059449	Narrow
		Candida osteomyelitis	10064699	
		Candida pneumonia	10053158	
		Candida retinitis	10068612	
		Candida sepsis	10053166	
		Candida urethritis	10081262	
		Candidiasis of trachea	10064459	
Cerebral candidiasis		10078126		
Endocarditis candida	10014669			

Category	Potential Opportunistic Infection	Preferred Term (MedDRA Version 22.1)	Preferred Term Code	Lilly Defined Classification	
		Gastrointestinal candidiasis	10017938		
		Hepatic candidiasis	10049653		
		Hepatosplenic candidiasis	10051590		
		Meningitis candida	10027205		
		Oesophageal candidiasis	10030154		
		Oral candidiasis	10030963		
		Oropharyngeal candidiasis	10050346		
		Peritoneal candidiasis	10056562		
		Splenic candidiasis	10051725		
		Systemic candida	10042938		
		Bladder candidiasis	10058523		Broad
		Candida infection	10074170		
		Candida test	10070453		
		Candida test positive	10070451		
		Mucocutaneous candidiasis ¹	10028080		
	Respiratory moniliasis	10038705			
	Coccidioidomycosis (II)	Coccidioides encephalitis	10054214	Narrow	
		Coccidioidomycosis	10009825		
		Cutaneous coccidioidomycosis	10068747		
		Meningitis coccidioides	10027207		
		None		Broad	
Cryptococcosis (II)	Cryptococcal cutaneous infection	10054216	Narrow		
	Cryptococcal fungaemia	10067112			
	Cryptococcosis	10011490			
	Disseminated cryptococcosis	10013439			
	Gastroenteritis cryptococcal	10011485			
	Meningitis cryptococcal	10027209			
	Neurocryptococcosis	10068368			
	Pneumonia cryptococcal	10067565			
	Cryptococcus test	10070456	Broad		
	Cryptococcus test positive	10070455			
Histoplasmosis (II)	Acute pulmonary histoplasmosis	10001027	Narrow		
	Chronic pulmonary histoplasmosis	10009115			

Category	Potential Opportunistic Infection	Preferred Term (MedDRA Version 22.1)	Preferred Term Code	Lilly Defined Classification
		Endocarditis histoplasma	10014676	
		Histoplasmosis	10020141	
		Histoplasmosis cutaneous	10049142	
		Histoplasmosis disseminated	10020144	
		Meningitis histoplasma	10027243	
		Pericarditis histoplasma	10034489	
		Retinitis histoplasma	10038912	
		Presumed ocular histoplasmosis syndrome	10063664	
	Microsporidiosis (IV)	Microsporidia infection	10053982	Narrow
		None		Broad
	Other invasive fungi: Mucormycosis (=zygomycosis) [Rhizopus, Mucor, and Lichtheimia], Scedosporium/ Pseudallescheria boydii , Fusarium (II)	Allescheriosis	10001754	Narrow
		Fusarium infection	10051919	
		Mucormycosis	10028098	
		Scedosporium infection	10059045	
		Pseudallescheria infection	10061919	
		Pseudallescheria sepsis	10058973	
	Paracoccidioides infections (V)	Paracoccidioides infection	10061906	Narrow
		None		Broad
	Penicillium marneffei (V)	Penicillium infection	10078580	Narrow
		None		Broad
	Pneumocystis jirovecii (II)	Pneumocystis jirovecii infection	10073756	Narrow
Pneumocystis jirovecii pneumonia		10073755		
Blood beta-D-glucan		10068725	Broad	
Blood beta-D-glucan abnormal		10051795		
Blood beta-D-glucan increased		10051793		
Gomori methenamine silver stain		10075549		
Carbon monoxide diffusing capacity decreased		10065906		
Carbon monoxide diffusing capacity		10071738		

Category	Potential Opportunistic Infection	Preferred Term (MedDRA Version 22.1)	Preferred Term Code	Lilly Defined Classification
		Pneumocystis test positive	10070454	
	Sporothrix schenckii (V)	Cutaneous sporotrichosis	10011676	Narrow
		Sporotrichosis	10041736	
		None		Broad
Viral	Cytomegalovirus disease (V)	Cytomegalovirus chorioretinitis	10048843	Narrow
		Cytomegalovirus colitis	10048983	
		Cytomegalovirus duodenitis	10049014	
		Cytomegalovirus enteritis	10049074	
		Cytomegalovirus enterocolitis	10049015	
		Cytomegalovirus gastritis	10049016	
		Cytomegalovirus gastroenteritis	10051349	
		Cytomegalovirus gastrointestinal infection	10052817	
		Cytomegalovirus gastrointestinal ulcer	10075619	
		Cytomegalovirus hepatitis	10011830	
		Cytomegalovirus infection	10011831	
		Cytomegalovirus mononucleosis	10011834	
		Cytomegalovirus mucocutaneous ulcer	10065036	
		Cytomegalovirus myelomeningoradiculitis	10065621	
		Cytomegalovirus myocarditis	10056261	
		Cytomegalovirus nephritis	10079095	
		Cytomegalovirus oesophagitis	10049018	
		Cytomegalovirus pancreatitis	10049566	
		Cytomegalovirus pericarditis	10056721	
		Cytomegalovirus syndrome	10056262	

Category	Potential Opportunistic Infection	Preferred Term (MedDRA Version 22.1)	Preferred Term Code	Lilly Defined Classification	
		Cytomegalovirus urinary tract infection	10051350		
		Cytomegalovirus viraemia	10058854		
		Disseminated cytomegaloviral infection	10049075		
		Encephalitis cytomegalovirus	10014586		
		Pneumonia cytomegaloviral	10035676		
		Cytomegalovirus test	10061806		Broad
		Cytomegalovirus test positive	10051620		
	HBV reactivation (IV)	None			Narrow
		Asymptomatic viral hepatitis	10063838		Broad
		Chronic hepatitis B	10008910		
		HBV-DNA polymerase increased	10058937		
		Hepatitis B	10019731		
		Hepatitis B antigen	10063414		
		Hepatitis B antigen positive	10063411		
		Hepatitis B core antigen	10051160		
		Hepatitis B core antigen positive	10052328		
		Hepatitis B DNA assay	10060027		
		Hepatitis B DNA assay positive	10060047		
		Hepatitis B DNA increased	10068379		
		Hepatitis B e antigen	10050914		
		Hepatitis B e antigen positive	10052329		
		Hepatitis B reactivation	10058827		
		Hepatitis B surface antigen	10050529		
		Hepatitis B surface antigen positive	10019742		
		Hepatitis B virus test	10068415		
		Hepatitis B virus test positive	10070217		
		Hepatitis A	10019780		

Category	Potential Opportunistic Infection	Preferred Term (MedDRA Version 22.1)	Preferred Term Code	Lilly Defined Classification
		Hepatitis post transfusion	10019791	
		Hepatitis viral	10019799	
		Withdrawal hepatitis	10071220	
Viral	HCV progression (V)	None		Narrow
		Chronic hepatitis C	10008912	Broad
		Hepatitis C	10019744	
		Hepatitis C RNA	10019748	
		Hepatitis C RNA fluctuation	10068727	
		Hepatitis C RNA increased	10068377	
		Hepatitis C RNA positive	10019750	
		Hepatitis C virus test	10068416	
		Hepatitis C virus test positive	10070218	
	Herpes simplex (IV)	Colitis herpes	10051782	Narrow
		Eczema herpeticum	10014197	
		Gastritis herpes	10051784	
		Herpes oesophagitis	10052330	
		Herpes sepsis	10058876	
		Herpes simplex colitis	10074239	
		Herpes simplex encephalitis	10019953	
		Herpes simplex gastritis	10074240	
		Herpes simplex hepatitis	10067389	
		Herpes simplex meningitis	10019956	
		Herpes simplex meningoencephalitis	10074247	
Herpes simplex meningomyelitis	10074250			
Herpes simplex necrotising retinopathy	10074252			
Herpes simplex oesophagitis	10074242			
Herpes simplex pneumonia	10065046			
Herpes simplex sepsis	10074246			
Herpes simplex visceral	10019963			
Meningitis herpes	10027242			
Meningoencephalitis herpetic	10027285			
Meningomyelitis herpes	10074249			

Category	Potential Opportunistic Infection	Preferred Term (MedDRA Version 22.1)	Preferred Term Code	Lilly Defined Classification	
		Pneumonia herpes viral	10035703		
		Genital herpes simplex	10073931		
		Herpes dermatitis	10062639		
		Herpes pharyngitis	10066888		
		Herpes simplex otitis externa	10019959		
		Herpes simplex pharyngitis	10074244		
		Ophthalmic herpes simplex	10073938		
		Proctitis herpes	10036780		
		Kaposi's varicelliform eruption	10051891		
		Herpes simplex test positive	10077969		Broad
		Herpes simplex	10019948		
		Herpes virus infection	10019973		
		Nasal herpes	10074936		
		Oral herpes	10067152		
		Genital herpes	10018150		
	Herpes zoster (any form) (II)	Disseminated varicella zoster vaccine virus infection	10076667	Narrow	
		Encephalitis post varicella	10014603		
		Genital herpes zoster	10072210		
		Herpes zoster	10019974		
		Herpes zoster cutaneous disseminated	10074297		
		Herpes zoster disseminated	10065038		
		Herpes zoster infection neurological	10061208		
		Herpes zoster meningitis	10074259		
		Herpes zoster meningoencephalitis	10074248		
		Herpes zoster meningomyelitis	10074251		
Herpes zoster meningoradiculitis	10079327				
Herpes zoster necrotising retinopathy	10074253				
Herpes zoster oticus	10063491				
Herpes zoster pharyngitis	10074245				

Category	Potential Opportunistic Infection	Preferred Term (MedDRA Version 22.1)	Preferred Term Code	Lilly Defined Classification	
		Necrotising herpetic retinopathy	10065119		
		Ophthalmic herpes zoster	10030865		
		Varicella	10046980		
		Varicella keratitis	10077496		
		Varicella post vaccine	10063522		
		Varicella zoster gastritis	10074241		
		Varicella zoster oesophagitis	10074243		
		Varicella zoster pneumonia	10074254		
		Varicella zoster virus infection	10075611		
		Herpes ophthalmic	10062004		
		Varicella virus test	10070444		Broad
		Varicella virus test positive	10070214		
	Human Polyomavirus infection including BK virus disease and PVAN (V), and Progressive Multifocal Leukoencephalopathy (IV)	BK virus infection	10055181	Narrow	
		Human polyomavirus infection	10057366		
		JC virus granule cell neuronopathy	10074361		
JC virus infection		10023163			
Polyomavirus-associated nephropathy		10065381			
Progressive multifocal leukoencephalopathy		10036807			
JC virus test		10068794	Broad		
Polyomavirus test		10075038			
Post-transplant lymphoproliferative disorder (EBV) (V)	Epstein-Barr virus associated lymphoproliferative disorder	10068349	Narrow		
		10051358			
	Epstein-Barr viraemia	10065110	Broad		
	Epstein-Barr virus associated lymphoma	10071441			
	Epstein-Barr virus infection	10015108			

Category	Potential Opportunistic Infection	Preferred Term (MedDRA Version 22.1)	Preferred Term Code	Lilly Defined Classification
		Lymphoproliferative disorder	10061232	
		Lymphoproliferative disorder in remission	10061233	
		Oral hairy leukoplakia	10030979	
Parasites	Trypanosoma cruzi infection (Chagas' Disease) (disseminated disease only) (V)	None		Narrow
		American trypanosomiasis	10001935	Broad
		Trypanosomiasis	10044707	
		Meningitis trypanosomal	10027258	
	Cryptosporidium species (chronic disease only) (IV)	Biliary tract infection cryptosporidial	10067319	Narrow
		Cryptosporidiosis infection	10011502	Broad
		Gastroenteritis cryptosporidial	10017899	
	Leishmaniasis (Visceral only) (IV)	Visceral leishmaniasis	10047505	Narrow
		Leishmaniasis	10024198	Broad
	Strongyloides (hyperinfection syndrome and disseminated forms only) (IV)	None		Narrow
		Strongyloidiasis	10042254	Broad
	Toxoplasmosis (IV)	Cerebral toxoplasmosis	10057854	Narrow
		Eye infection toxoplasmal	10015939	
		Hepatitis toxoplasmal	10019798	
		Meningitis toxoplasmal	10048848	
		Myocarditis toxoplasmal	10028617	
		Pneumonia toxoplasmal	10067566	
Toxoplasma serology		10050941	Broad	
Toxoplasmosis	10044272			
Non-specific terms	Non-specific terms	None		Narrow
		Delftia acidovorans infection	10081339	
		Sphingomonas paucimobilis bacteraemia	10081563	
	Central nervous system immune reconstitution inflammatory response	10080100	Broad	
	Abscess fungal	10000269		
	Alternaria infection	10054207		
	Arthritis fungal	10060966		

Category	Potential Opportunistic Infection	Preferred Term (MedDRA Version 22.1)	Preferred Term Code	Lilly Defined Classification
		Biliary tract infection fungal	10065203	
		Central nervous system fungal infection	10072805	
		Cerebral fungal infection	10049657	
		Encephalitis fungal	10065170	
		Erythema induratum	10015213	
		Eye infection fungal	10015933	
		Fungaemia	10017523	
		Fungal abscess central nervous system	10017524	
		Fungal endocarditis	10017529	
		Fungal labyrinthitis	10065174	
		Fungal oesophagitis	10049656	
		Fungal peritonitis	10061138	
		Fungal pharyngitis	10076516	
		Fungal retinitis	10068613	
		Fungal sepsis	10058872	
		Fungal urethritis	10081163	
		Hepatic infection fungal	10065217	
		Meningitis fungal	10027236	
		Mycotic endophthalmitis	10063202	
		Myocarditis mycotic	10059026	
		Oral fungal infection	10061324	
		Oropharyngitis fungal	10061891	
		Osteomyelitis fungal	10065239	
		Otitis media fungal	10065175	
		Pancreatitis fungal	10065190	
		Pericarditis fungal	10065220	
		Phaeophycomycosis	10034799	
		Pneumonia fungal	10061354	
		Pulmonary mycosis	10037422	
		Pulmonary trichosporonosis	10068184	
Sinusitis fungal	10058678			
Splenic infection fungal	10065194			
Systemic mycosis	10052366			
Pneumonia	Infective Pneumonia SMQ	All PTs (exclude COVID-19 and influenza PTs)	20000231	Narrow

Abbreviations: DNA = deoxyribonucleic acid; EBV= Epstein-Barr virus; HBV = hepatitis B virus; MedDRA = Medical Dictionary for Regulatory Activities; PT = Preferred Term; PVAN = Polyomavirus-associated nephropathy; SMQ = Standardized MedDRA Query.

Appendix 5. List of MedDRA Preferred Terms for Elevated or Increased Lipids from the Dyslipidemia SMQ (SMQ 2000026)

Preferred Term (MedDRA Version 20.0)	Preferred Term Code
Apolipoprotein B/Apolipoprotein A-1 ratio increased	10065516
Autoimmune hyperlipidaemia	10071577
Blood cholesterol abnormal	10005423
Blood cholesterol increased	10005425
Blood triglycerides abnormal	10005837
Blood triglycerides increased	10005839
Diabetic dyslipidaemia	10070901
Dyslipidaemia	10058108
Familial hypertriglyceridaemia	10059183
Fat overload syndrome	10074028
High density lipoprotein abnormal	10020051
High density lipoprotein decreased	10020060
High density lipoprotein increased	10020061
Hypercholesterolaemia	10020603
Hyperlipidaemia	10062060
Hypertriglyceridaemia	10020869
Hypo HDL cholesterolaemia	10068961
Intermediate density lipoprotein increased	10064236
LDL/HDL ratio increased	10049030
Lipid metabolism disorder	10061227
Lipids abnormal	10024588
Lipids increased	10024592
Lipoprotein (a) abnormal	10054023
Lipoprotein (a) increased	10054009
Low density lipoprotein abnormal	10024901
Low density lipoprotein increased	10024910
Non-high-density lipoprotein cholesterol increased	10063967
Remnant hyperlipidaemia	10038316
Total cholesterol/HDL ratio abnormal	10058633
Total cholesterol/HDL ratio increased	10058630

Preferred Term (MedDRA Version 20.0)	Preferred Term Code
Type I hyperlipidaemia	10060749
Type II hyperlipidaemia	10045254
Type IIa hyperlipidaemia	10045261
Type IIb hyperlipidaemia	10045263
Type III hyperlipidaemia	10060751
Type IV hyperlipidaemia	10060753
Type V hyperlipidaemia	10060755
Very low density lipoprotein abnormal	10047352
Very low density lipoprotein increased	10047361

Abbreviation: MedDRA = Medical Dictionary for Regulatory Activities.

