8.3.6.2. Serious Infections and Opportunistic Infections

Completion of the Infection eCRF page is required for each infection reported as an AE or SAE. The sponsor will identify infections considered to be opportunistic based on the article by Winthrop et al. (2015) (Appendix 10.6).

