	Vibriosis (invasive disease due to Vibrio vulnificus)
Viral	
	BK virus disease including polyomavirus-associated nephropathy
	Cytomegalovirus disease
	Hepatitis B virus reactivation
	Hepatitis C virus progression
	Herpes simplex (invasive disease only)
	Herpes zoster (any form)
	Post-transplant lymphoproliferative disorder (Epstein-Barr virus)
	Progressive multifocal leukoencephalopathy (PML), John Cunningham (JC) virus
Fungal	
	Aspergillosis (invasive disease only)
	Blastomycosis
	Candidiasis (invasive disease or oropharyngeal, esophageal. Not isolated lingual.)
	Coccidioidomycosis
	Cryptococcosis
	Histoplasmosis
	Paracoccidioides infections
	Penicilliosis
	Pneumocystosis
	Sporotrichosis
	Other invasive molds: Mucormycosis (zygomycosis) (Rhizopus , Mucor , and Lichtheimia), Scedosporium/Pseudallescheria boydii , Fusarium
Parasitic	
	Leishmaniasis (visceral only)
	Strongyloidosis (hyperinfection syndrome or disseminated disease)
	Microsporidiosis
	Toxoplasmosis
	Trypanosoma cruzi infection (Chagas' disease progression) (disseminated disease only)
	Cryptosporidiosis (chronic disease only)

Source: Adapted from Winthrop et al. (2015).

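### SAP Appendix 4 files the exact term for hepatitis B reactivation as Broad, leaves that row with no Narrow term, and carries two plainly misfiled Broad terms

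*SAP*

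**What the plan says.** **Protocol.** Section 8.3.6.2 gives the classification to the sponsor: "The sponsor will identify infections considered to be opportunistic based on the article" cited there, with a pointer to Appendix 6 (Section 10.6). That appendix lists "Hepatitis B virus reactivation" among its viral examples and attaches no severity or site condition to it. It also says that its list is open and is there to help investigators recognise such infections.

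**SAP.** Appendix 4 maps categories of potential opportunistic infection to MedDRA preferred terms, each classed Narrow or Broad.
- The row opening "HBV reactivation (IV" shows None against Narrow. Its Broad block contains "Hepatitis B reactivation" (10058827), several assay names, some unspecific hepatitis terms, and hepatitis A (10019780).
- The Broad block for nontuberculous mycobacterial disease ends with "Ureaplasma ulvovaginitis" (10081280).
- A separate Pneumonia category takes the "Infective Pneumonia SMQ" as Narrow, with the rule "All PTs (exclude COVID-19 and influenza PTs").

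The readable SAP does not show how Narrow and Broad are used. The text just before Section 6.19.3.3 is blacked out.

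**The concern.** A Narrow set normally holds the terms that identify the event by themselves, and a Broad set holds terms that only raise the possibility. A term that names HBV reactivation belongs in the first group, yet it is filed beside test names that carry no result.

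HBV reactivation is also an event this trial looks for. Protocol Section 8.2.7 requires HBV DNA retesting at least every 3 months in anti-HBc-positive participants. Sections 7.1.1 and 7.1.2.1 tie decisions on study drug to the result, and the notes to the schema in Section 1.2 describe Visit 802 as being for HBV DNA testing. If the opportunistic-infection summary were built on Narrow terms, a case found and coded exactly as intended would not be in it. The two misfiled terms work the other way: they would add an unrelated infection to a summary that includes Broad terms.

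**Working it through.** No figure in the plan bears on this, so the check is a line-by-line comparison of SAP Appendix 4 with Protocol Appendix 6, with hand counts.

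**1. Coverage.** Protocol Appendix 6 has 10 bacterial + 8 viral + 11 fungal + 6 parasitic = 35 entries. Each has a matching row in SAP Appendix 4 (BK virus disease and progressive multifocal leukoencephalopathy share one). Nothing on the protocol's list is absent from the SAP's list.

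**2. Rows with no Narrow term.** There are five of 35.

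| Protocol entry | Condition in the protocol | Does a listed Broad term repeat the event by name? |
|---|---|---|
| Vibriosis | invasive, *V. vulnificus* | No (vibrio gastroenteritis, positive vibrio test) |
| HCV progression | progression | No (hepatitis C, chronic hepatitis C, RNA terms) |
| *T. cruzi* infection | disseminated | No (trypanosomiasis terms without dissemination) |
| Strongyloidosis | hyperinfection or disseminated | No (plain strongyloidiasis) |
| HBV reactivation | none beyond reactivation itself | **Yes** (10058827) |

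For the first four, None is understandable, because no listed term is specific enough. HBV is the one row of the five where the specific term is listed and is still Broad.

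**3. The appendix's own practice.** Terms that name a listed event are generally Narrow: progressive multifocal leukoencephalopathy, polyomavirus-associated nephropathy, visceral leishmaniasis, herpes zoster, nocardiosis. The practice is not uniform. Plain toxoplasmosis follows the Broad label although the protocol lists it without a condition. That row, however, still has six organ-specific Narrow terms, whereas the HBV row has none.

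**4. The HBV row, counted.** Narrow 0, Broad 22. After the proposed edits: Narrow 1, and Broad 22 − 1 (moved) − 1 (hepatitis A deleted) = 20. The Broad block for nontuberculous mycobacterial disease goes from 6 terms to 5.

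**5. Effect by possible use of the list.**

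| Use | A coded HBV reactivation | Hepatitis A and the Ureaplasma term |
|---|---|---|
| Narrow only | omitted | not counted |
| Narrow plus Broad | counted | counted under the wrong infection |
| Term search, then sponsor review | depends on whether the search includes Broad | can be removed at review |

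Hepatitis A is a different virus from the one the row is about, so it differs from the row's unspecific entries such as viral hepatitis, which could hide an HBV case. The Ureaplasma term names a different organism from the mycobacteria.

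**The case against.** The strongest reply is that the harm depends on text nobody outside the sponsor can read. The appendix title speaks of potential infections, and the protocol has the sponsor make the classification. The SAP also uses search-then-review elsewhere, for malignancies (Section 6.19.3.3) and for hepatic terms (Section 6.19.5.1). If this list feeds such a review with Broad terms included, a wide net is its purpose and an HBV reactivation reaches the reviewer. That stands, and it is why the effect is stated conditionally.

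It is also fair that HBV is not the only row without a Narrow term, that the practice on exact terms has the toxoplasmosis exception, and that a treatment-emergent HBV reactivation would still appear by preferred term in the tables of Section 6.19.2.1. Some column labels in this table are displaced or absent in the copy read (aspergillosis shows none), but the HBV row's None/Narrow entry and the Broad label after it are legible.

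Several stronger readings are tempting and are not supported:
- *The SAP list fails to match the protocol's list.* All 35 entries have a row, and the protocol's list is open.
- *Every pneumonia counts as opportunistic.* COVID-19 and influenza terms are excluded. Classing the rest as Narrow is a choice open to the sponsor under a non-exhaustive list, and pneumonia already has its own category.
- *The comparison between arms is misstated whichever scope is used.* Neither the scope nor the absence of a review step can be read from the documents.
- *The list is frozen at MedDRA 22.1.* The appendix carries that version and Section 6.19.2.1 codes in the version current at lock, but an update clause could sit in the redacted text.
- *"Bovine tuberculosis" under nontuberculous disease distorts the count.* It is Narrow where it stands and would be Narrow under tuberculosis, so no overall total changes.

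**Conclusion.** The point holds as a minor correction to one appendix. The row for HBV reactivation has 0 Narrow terms out of 22, and the term that repeats the protocol's event by name is among the Broad ones. Two further Broad terms, hepatitis A and the Ureaplasma term, plainly do not belong to the infections they are filed under.

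The consequence is conditional on the redacted section. Under a Narrow-only summary a coded HBV reactivation would be left out; under Narrow plus Broad, two unrelated terms would be let in. The number of participants affected cannot be estimated, since the documents give no event rates. It is likely to be small: participants positive for HBsAg or HBV DNA are excluded at screening, and only anti-HBc-positive participants are retested. No efficacy endpoint is touched.

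The correction is still worth making, because each edit improves one plausible use of the list and harms none.

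**What to change.** In SAP Appendix 4, before unblinding:
1. Move 10058827 from Broad to Narrow in the HBV reactivation row.
2. Delete hepatitis A (10019780) from that row.
3. Delete the Ureaplasma term (10081280) from the row for nontuberculous mycobacterial disease.

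The placement of plain toxoplasmosis can be confirmed in the same pass. No change to the pneumonia classification is required; at most, show the pneumonia terms as their own row in the output so that they can be told apart from the named pathogens.

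The cost is an edit to one appendix and to the matching search list in the programs. No data collection, visit or efficacy analysis changes, and events coded to the deleted terms stay in the general adverse event tables.
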